10.2. Case Report Form

After the protocol approval, the site will be trained on the protocol and the data collection system by template of Case Report Form (CRF) with the appropriate documentations.

The data collection will take place through the previously mentioned phases within three months from the first patient entered till the last patient data collected with the optimum tracking and quality control for the patients' records and registries to ensure the validity of the collected data.

11. SOURCE DATA

Source documents are original documents and records from which participants' CRF data are obtained. These include, but are not limited to, hospital records (from which medical history and

previous and concurrent medication may be summarized into the CRF), clinical and office charts, laboratory and pharmacy records...etc, ...

All documents will be stored safely in a secured room. In all study-specific documents, other than the signed informed consent, the patient will be referred to by the patient initials and patient number i.e. patient ID.

12. TREATMENT OF TRIAL PARTICIPANTS

12.1. Description of Study Medication(s)

Because thrombin plays a central role in thrombogenesis, the goal of most treatment regimens is to block thrombin generation or inhibit its activity.

1- r-Hirudin binds directly with thrombin to its active & fibrinogen binding site.

2- r-hirudin does not require access to heparin binding site & can thus neutralize clot bound thrombin. Hence, down regulating thrombin generation & potentially enhancing early revascularization.

Direct thrombin inhibitors were developed to overcome the inability of the heparin/antithrombin complex to inactivate bound thrombin. In contrast to heparin and low-molecular-weight heparin, which catalyze the inactivation of thrombin and activated factor X (factor Xa) by antithrombin, direct thrombin inhibitors bind to thrombin and block its interaction with its substrates.

II- They do not bind to plasma proteins, direct thrombin inhibitors produce a more predictable anticoagulant response than heparin.

III- Unlike heparin, direct thrombin inhibitors do not interact with platelet factor 4 or high-molecular-weight multimers of von Willebrand factor. Consequently, the activity of direct thrombin inhibitors in the vicinity of a platelet-rich thrombus is not compromised.

IV- Finally, thrombin bound to fibrin or fibrin degradation products is susceptible to inactivation by direct thrombin inhibitors. Because the active site of thrombin is not involved in the interaction of the enzyme with fibrin, it remains accessible to active site-directed thrombin inhibitors. Consequently, these agents inactivate fibrin-bound thrombin without displacing the enzyme from fibrin. In contrast, bivalent thrombin inhibitors, such as Hirudin and bivalirudin, displace bound thrombin during the inhibition reaction by competing with fibrin for access to exosite 1 on thrombin.

Dose of Thrombexx®:

In DVT Prophylaxis: 15 mg twice daily, subcutaneous for 15 days

In case of renal insufficiency, the dose is titrated because r-Hirudin is excreted renally.

According to Creatinine clearance:

Creatinine clearance > 31-60 ml/min (5 mg s.c twice daily)

Creatinine clearance < 31 ml/min (1.7 mg s.c twice daily)

In case of patients who will receive spinal anesthesia; Thrombexx will be given 8-10 hours before puncture/catheter and 2-4 hours after puncture/catheter manipulation or removal, as per European Guidelines.

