Statistical analysis	
- Descriptive analysis: All statistical tests used a significance level of P=0.05, two tailed tests are performed for all analyses used statistical testing. Descriptive analysis for quantitative data will include count, mean with 95% CI, standard deviation, median, minimum and maximum. For qualitative categorical variables; frequency and percentage and 95% confidence interval will be applied.

Stopping rules	
DVT PE Major bleeding Allergy APTT value increases by 2-2.5 folds According to investigator evaluation

Table of Contents

Title Page	1
1. Synopsis	2
Table of Contents	6
2. LIST OF ABBREVIATIONS	9
3. SIGNATURE(S) PAGE	10
4. INTRODUCTION	11
4.1. Background	11
4.2. Correlative studies:	11
4.3. Study Rationale	12
5. STUDY OBJECTIVES	12
5.1. Primary Objectives	12
5.2. Secondary objectives	12
6. TRIAL DESIGN	12
6.1. The pre-operative Phase	12
6.2. The operative Phase	13
6.3. The Follow-up Phase	13
7. FLOW CHARTS:	13
7.1. STUDY FLOW CHARTS:	13
7.2. STUDY PHASES	14
8. STUDY OUTCOME MEASURES	15
8.1. Primary Endpoints	15
8.2. Secondary Endpoints	16
9. STUDY POPULATION	16
9.1. Recruitment strategy:	16
9.2. Inclusion Criteria	16
9.3. Exclusion Criteria	16
10. STUDY PROCEDURE:	17
10.1. Selection of the study population:	17
10.2. Case Report Form	17
11. SOURCE DATA	17

12.	TREATMENT OF TRIAL PARTICIPANTS	18
12.1.	Description of Study Medication(s)	18
12.2.	Concomitant Medication (if applicable).....	19
13.	DATA COLLECTION	19
15.1.	DATA MANAGEMENT	20
15.2.	AMENDMENT TO THE PROTOCOL.....	20
15.2.1.	Protocol Deviations	20
15.2.2.	Onsite Audits.....	20
15.2.3.	Study Monitoring	21
15.3.	PREMATURE DISCONTINUATION OF STUDY.....	22
16.	SAFETY REPORTING AND DEFINITIONS	22
16.1.	Adverse Events Monitoring.....	22
16.2.	Reporting Period.....	23
16.3.	Adverse Event (AE):	23
16.4.	Serious Adverse Events	24
16.4.1.	Instructions for Reporting Serious Adverse Events	24
17.	STATISTICAL METHODOLOGY	24
17.1.	Determination of Sample Size.....	24
17.2.	Analysis Variables:.....	25
17.2.1.	Primary analysis variables:.....	25
17.2.2.	Secondary analysis variables:.....	25
17.2.3.	Statistical Method:.....	25
17.2.4.	Interim Analysis	25
18.	ETHICS.....	25
18.1.	INDEPENDENT ETHICS COMMITTEE (IEC) OR INSTITIUTIONAL REVIEW BOARD (IRB).....	25
18.2.	Ethical principles:	26
18.3.	Laws and regulations:	26
18.4.	PATIENT INFORMATION AND CONSENT	26
18.5.	DISCONTINUATION OF THE STUDY	27
18.5.1.	PREMATURE DISCONTINUATION OF STUDY	27

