6.1. The pre-operative Phase

During this phase, patients will be screened for fulfillment of the inclusion and exclusion. Patient's demography, history of diseases will be collected, laboratory investigations such as Hemoglobin count, Platelets count, APTT, INR, SGPT, SGOT, Serum albumin, serum Bilirubin, serum creatinine and random blood glucose and pregnancy test for females in childbearing period.

APTT should be done before IMP administration, in addition to the patient's data of Thrombexx® administration regimen decided by the treating investigator according to the standard clinical practice or as prescribed in the usual manner in accordance with the terms of the local marketing authorization with regards to dose, population and indication (and within the approved label).

Medical history and Medication history should also be collected.

Main complaint of the patient during routine physical examination should be recorded

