6.3. The Follow-up Phase

During this phase, which is approximately 15 days, PE which is confirmed by spiral CT chest, any new DVT appears also to be confirmed by Doppler ultrasound, Bleeding assessment, APTT will be done on days 1, 8 & 15, concomitant medications, Hospital stay and any adverse event data will all be recorded

7. FLOW CHARTS:

7.1. STUDY FLOW CHARTS:

Activity	Pre-operative phase (Screening)	Operative phase (Day 0)	Follow-up 1 (Day 1)	Follow-up 2 (Day 8)	Follow-up 3/ End of Study (Day 15)
ICF Signature	×				
Inclusion/Exclusion Criteria	×				
Demographic Data	×				
Medical History	×				
Vital signs	×				
Concomitant Medication	×				
Physical Examination	×				

Laboratory investigation	×		×	×	×
Type of surgery		×			
Assessment of bleeding		×	×	×	
IMP Administration		×	×	×	×
Assessment of DVT			×	×	×
Assessment of PE			×	×	×
Assessment of therapeutic response					×
APTT	×	×	×	×	×
Adverse Event		×	×	×	×
Study completion					×

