7.2. STUDY PHASES

The study consists of 3 phases:

Visit 1: Preoperative phase (screening)

- ❖ Patient Screening (Check eligibility)
- ❖ Signed ICF
- ❖ Gathering Patient Information as Demographic, Vital Signs, BMI, Physical Examination, Medical History, Concomitant medications
- ❖ Laboratory Investigations (Hb, PLt count, APTT, INR, SGPT, SGOT, Serum Albumin, Serum Bilirubin, serum creatinine, Creatinine clearance, Random blood sugar)
- ❖ Patients main complaint (Knee, Hip)

Operative phase (Day 0)

Patient Data to be collected:

- ❖ Type , Date of surgery
- ❖ Type of anaesthesia
- ❖ Patient position
- ❖ Type of prosthesis
- ❖ Blood transfusion

Start of IMP administration.

APTT 4 & 8 hours after IMP administration

Visit 2: Post operative phase (Follow-up 1 (Day 1))

- ❖ Assessment of bleeding
- ❖ Type of blood transfusions
- ❖ Assessment of DVT
- ❖ Routine bilateral compression Doppler (confirmation for DVT)
- ❖ Assessment of PE
- ❖ Spiral CT (confirming PE)
- ❖ IMP administration
- ❖ Laboratory investigations (Hb%, Platelets count)
- ❖ APTT

Assessment will be done in the hospital, as post-operative period before discharge from hospital.

Visit 3: Follow-up 2 (Day 8)

- ❖ Assessment of bleeding
- ❖ Type of blood transfusions
- ❖ Assessment of DVT
- ❖ Routine bilateral compression Doppler (confirmation for DVT)
- ❖ Assessment of PE
- ❖ Spiral CT (confirming PE)
- ❖ IMP administration
- ❖ Laboratory investigations (Hb%, Platelets count)
- ❖ APTT

Assessment in day 8 will be done from outpatient clinic in most patients.

Visit 4: Follow-up 3/ End of Study (Day 15)

- ❖ Assessment of bleeding
- ❖ Type of blood transfusions
- ❖ Assessment of DVT
- ❖ Laboratory Investigations
- ❖ Routine bilateral compression Doppler (confirmation for DVT)
- ❖ Assessment of PE
- ❖ Spiral CT (confirming PE)
- ❖ APTT
- ❖ End of Study

Assessment in day 15 will be done from outpatient clinic.

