15.3. PREMATURE DISCONTINUATION OF STUDY

The sponsor may prematurely terminate the trial if any of the following situations occurs:

APTT value of the subject increased by 2-2.5 folds.

Comprehensive deficiency in the recorded data or protocol compliance so that the results of the study cannot be reliably assessed.

Occurrence of AEs necessitating termination such as major bleeding, DVT, PE, allergy or for any other reason according to investigator evaluation.

The IRB/IEC changes its opinion regarding the safety/efficacy/relevance of the compound.

Regulatory authority decision.

If the trial is prematurely terminated or suspended for any reason, the investigators and subsequently the trial subjects will be informed promptly, standard therapy and follow-up for subjects will be assured and, where required by the applicable regulatory requirement(s), the relevant regulatory authority(s) will be informed. The IRB/IEC and all trials sites will be informed promptly and provided with a detailed written explanation for the termination or suspension. As directed by Minapharm, all study materials must be collected and all CRFs completed to the greatest extent possible.

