18.5.1. PREMATURE DISCONTINUATION OF STUDY

Minapharm may prematurely terminate the trial if any of the following situations occurs:

APTT value for the subject increases by 2-2.5 folds

Comprehensive deficiency in the recorded data or protocol compliance so that the results of the study cannot be reliably assessed.

Occurrence of AEs necessitating termination.

Minapharm terminates the development plan for the compound.

The IRB/IEC changes its opinion regarding the safety/efficacy/relevance of the compound.

Regulatory authority decision.

If the trial is prematurely terminated or suspended for any reason, the investigators and subsequently the trial subjects will be informed promptly, standard therapy and follow-up for subjects will be assured and, where required by the applicable regulatory requirement(s), the relevant regulatory authority(s) will be informed. The IRB/IEC and all trials sites will be informed promptly and provided with a detailed written explanation for the termination or suspension. As directed by Minapharm, all study materials must be collected and all CRFs completed to the greatest extent possible.

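### The dose is set by creatinine clearance over a 15-day course, but no renal test is named between surgery and Day 15

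*Protocol*

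**What the plan says.** Protocol section 12.1 gives 15 mg subcutaneously twice daily for 15 days. It lowers this to 5 mg twice daily for a clearance of 31-60 ml/min and to 1.7 mg twice daily below 31, on the ground that "In case of renal insufficiency, the dose is titrated because r-Hirudin is excreted renally".

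The Visit 1 list in section 7.2 includes "serum creatinine, Creatinine clearance, Random blood sugar", and section 6.1 also names serum creatinine before surgery. For Days 1 and 8 the list in 7.2 shrinks to "Laboratory investigations (Hb%, Platelets count" and closes there, with APTT on its own line. Day 15 mentions laboratory work without naming tests. The flow chart in 7.1 has one row, "Laboratory investigation", marked at screening and Days 1, 8 and 15, with no content.

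Section 6.1 describes the regimen as an "administration regimen decided by the treating investigator according to the standard clinical practice", or as prescribed under the local marketing authorisation and within the approved label.

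The synopsis stopping rules include "APTT value increases by 2-2.5 folds". Sections 15.3 and 18.5.1 repeat the trigger at trial level. In 15.3 the lead-in is "The sponsor may prematurely terminate the trial if any of the following situations occurs", and in 18.5.1 the item reads "APTT value for the subject increases by 2-2.5 folds".

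**The concern.** Clearance is the protocol's own dosing variable, and the course runs for two weeks after major surgery. The plan measures that variable once, before the operation, and names no later test that would show it had changed. Section 9.3 has no renal exclusion and the two lower bands presuppose patients with renal impairment, so patients close to a cut-off can enrol.

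What is at stake is individual safety on an anticoagulant. If clearance drops a band after surgery, a site that follows the plan exactly would keep giving the higher dose. Major bleeding is the secondary endpoint.

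**Working it through.** The plan states no figure on this point, so the check compares the schedule with the dose rule.

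**1. Named tests by visit (protocol 6.1, 6.2, 7.1, 7.2; SAP Tables 6, 10, 14, 15)**

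| Time | Creatinine / clearance named? | Other blood tests named |
|---|---|---|
| Screening | Yes | Hb, platelets, APTT, INR, liver tests, glucose |
| Day 0 (4 h and 8 h after first dose) | No | APTT |
| Day 1 | No | Hb, platelets, APTT |
| Day 8 | No | Hb, platelets, APTT |
| Day 15 | Panel not itemised | APTT |

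The SAP agrees. Creatinine and clearance appear only in the baseline Table 6. The follow-up blood tables are APTT (10), Hb (14) and platelets (15).

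**2. Ratio of the dose given to the dose listed after a fall**

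- From above 60 into 31-60: 15 / 5 = 3.0
- From 31-60 to below 31: 5 / 1.7 = 2.9
- From above 60 to below 31: 15 / 1.7 = 8.8

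**3. Ceiling on the excess.** The course has 2 x 15 = 30 doses, and Day 1 to Day 15 covers 14 x 2 = 28. Suppose the fall is present from Day 1 and nobody reacts before the end:

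- 28 x (15 - 5) = 280 mg
- 28 x (5 - 1.7) = 92.4 mg
- 28 x (15 - 1.7) = 372.4 mg

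These are upper bounds, because APTT or clinical review may lead to action sooner.

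**4. How much creatinine must rise.** The protocol names no clearance formula. Assume calculated clearance is inversely proportional to serum creatinine, so the rise needed is (starting clearance / cut-off) - 1.

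| Start (ml/min) | Cut-off | Rise needed |
|---|---|---|
| 65 | 60 | 65/60 - 1 = 8% |
| 70 | 60 | 70/60 - 1 = 17% |
| 80 | 60 | 80/60 - 1 = 33% |
| 90 | 60 | 90/60 - 1 = 50% |
| 35 | 31 | 35/31 - 1 = 13% |
| 40 | 31 | 40/31 - 1 = 29% |
| 45 | 31 | 45/31 - 1 = 45% |

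The 8.8-fold case needs a rise of more than 60/31 - 1 = 94%, so it is an extreme.

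**5. The same sensitivity works in reverse.** A patient at 58 ml/min on 5 mg whose creatinine drops 5% calculates to 58 / 0.95 = 61. Re-applying the table in both directions would triple that patient's dose to 15 mg. Any re-dosing rule should therefore allow reductions only.

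**6. Band edges.** The middle band is written as above 31 up to 60 and the lowest as below 31, so a clearance of exactly 31 has no dose.

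**The case against.** The strongest reply is that patients are monitored by other means. APTT is taken at 4 and 8 hours and on Days 1, 8 and 15, and a 2-2.5 fold rise is a stopping criterion. The synopsis also allows stopping on the investigator's evaluation. Section 16.1 has additional investigations recorded for adverse events, and 16.4.1 asks for copies of examinations for serious ones. Section 6.1 ties the regimen to standard practice and the approved label, and can reasonably be read as making the 12.1 table a starting-dose rule.

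Much of this stands, and a reader might infer from the gap that patients are unmonitored, which would be wrong. But these safeguards are partial. APTT can signal excess effect but cannot place a patient in a clearance band. The response listed for a raised APTT is to stop, and no text directs a dose reduction. The label is not among the documents, so whether it calls for renal monitoring is unknown; the dosing that protocol 4.1 takes from the package insert has a 12-day maximum, against 15 days here. Investigators may order creatinine, but nothing requires it, and Day 8 is an outpatient visit for most patients. If 12.1 is only a starting-dose rule, a later fall would still go unseen.

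A reader might also infer damage to a planned analysis of bleeding by current renal function. The documents do not support that. Section 5.2 lists baseline characteristics, dose, duration and concomitant medication as predictive factors, and the SAP contains no such analysis. Nor can one say by how much repeat testing would cut the excess dose, since that depends on how sites react with and without it.

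**Conclusion.** The point holds as a gap in safety monitoring that is cheap to close. Under the plan as written, no named renal test before Day 15 would reveal a post-operative fall into a lower dose band. A patient affected could remain on about three times the dose listed for that clearance.

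The ratios follow directly from 12.1. The creatinine rises rest on the inverse-proportion assumption, and the milligram totals on nobody reacting. The documents give no frequency of post-operative renal decline, so neither the number of patients affected nor any resulting number of bleeds can be derived. It would go too far to infer that overdosing is likely or that the trial is unsafe.

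**What to change.** - **Section 7.2:** add serum creatinine with calculated clearance to the Day 1 and Day 8 laboratory lists, using the blood already being drawn, and itemise Day 15.
- **CRF:** record clearance and current dose at each visit. The subject listings in 15.1 then cover reporting.
- **Section 12.1:** add wording such as: *If a post-operative creatinine clearance falls into a lower band, the dose is reduced to that band; the dose is not raised on the basis of a post-operative value. Creatinine is also measured if renal decline is suspected or the patient bleeds.*
- **Section 12.1:** assign a clearance of exactly 31 ml/min to a band.
- **Stopping rules:** state that the APTT rule applies regardless of clearance, so that the two rules do not compete.

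**Cost:** about 2 x 100 = 200 routine assays, occasional for-cause tests, a CRF change and an amendment approved by the IRB/IEC; no new visit.

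**Downsides:** some patients near a cut-off may have the dose lowered because of assay variation alone, which reduces their prophylaxis. A fall just after Day 1 can still go unseen until Day 8 (7 x 2 = 14 doses) unless testing is prompted clinically.

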Title Page

A Prospective, Single- Center, Phase IV Interventional, Single Arm **T**rial for the
Evaluation of subcutaneous recombinant **H**irudin 15 mg (RB variant) in
prophylaxis of Deep Vein Thrombosis (**DVT**) post major orthopedic operations

Principle Investigator: [name]

Sub Investigator: [name]

Study Site: Alexandria University

Protocol Name: THRIVE-DVT

Protocol Number: Sub-Thromb-001

Version:1.0, amendment 1

Date: 25th of January, 2022

CONFIDENTIALITY STATEMENT

This study was performed in compliance with Good Clinical Practice (GCP), including the archiving of essential documents. This report has been prepared in accordance with ICH Harmonized Tripartite Guideline on the Structure and Content of Clinical Study Reports, dated November 1995.

Any and all information presented in this document shall be treated as confidential and shall remain the exclusive property of **Minapharm Pharmaceuticals** (or any of its affiliated companies). The use of such confidential information must be restricted to the recipients for the agreed purpose and must be disclosed, published or otherwise communicated to any unauthorized persons, for any reasons, in any form whatsoever without the prior written consent of **Minapharm Pharmaceuticals** (or the concerned affiliate company); "Affiliate Company" means any corporation, partnership or other entity which at the date of communication or afterwards with **Minapharm Pharmaceuticals**

1. Synopsis

Title	Description
Study Title	Prospective, Single- Center, Interventional, Single Arm Trial for the Evaluation of subcutaneous recombinant Hirudin 15 mg (RB variant) in prophylaxis of Deep Vein Thrombosis (DVT) post major orthopedic operations
Study number	Sub-Thromb-001
Study Phase	Phase IV
Study Design	Prospective, Single arm, single-center
Study population	Patients undergoing major orthopedic operations
Study procedures	
Drug: r-Hirudin Other Name: Thrombexx
 
100 Patients will be treated with r-Hirudin (Thrombexx) for a total of 15 days beginning with 15 mg BID s.c starting 6 hours after surgery or upon adequate hemostasis and continued until end of study.

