
Study medication
	
Thrombexx ;
 
Because thrombin plays a central role in thrombogenesis, the goal of most treatment regimens is to block thrombin generation or inhibit its activity.
 
 1- r-Hirudin binds directly with thrombin to its active & fibrinogen binding site. 2- r-hirudin does not require access to heparin binding site & can thus neutralize clot bound thrombin. Hence, down regulating thrombin generation & potentially enhancing early revascularization. 
Direct thrombin inhibitors were developed to overcome the inability of the heparin/ antithrombin complex to inactivate bound thrombin. In contrast to heparin and low-molecular-weight heparin, which catalyze the inactivation of thrombin and activated factor X (factor Xa) by antithrombin, direct thrombin inhibitors bind to thrombin and block its interaction with its substrates.
 
II- They do not bind to plasma proteins; direct thrombin inhibitors produce a more predictable anticoagulant response than heparin.
 
III- Unlike heparin, direct thrombin inhibitors do not interact with platelet factor 4 or high-molecular-weight multimers of von Willebrand factor. Consequently, the activity of direct thrombin inhibitors in the vicinity of a platelet-rich thrombus is not compromised.
 
IV- Finally, thrombin bound to fibrin or fibrin degradation products is susceptible to inactivation by direct thrombin inhibitors. Because the active site of thrombin is not involved in the interaction of the enzyme with fibrin, it remains accessible to active site-directed thrombin inhibitors. Consequently, these agents inactivate fibrin-bound thrombin without displacing the enzyme from fibrin. In contrast, bivalent thrombin inhibitors, such as Hirudin and bivalirudin, displace bound thrombin during the inhibition reaction by competing with fibrin for access to exosite 1 on thrombin.

	
Dose: In DVT Prophylaxis: 15 mg twice daily, subcutaneous for 15 days
 
In case of renal insufficiency, the dose is titrated because r-Hirudin is excreted renally. According to Creatinine clearance: •Creatinine clearance > 31-60 ml/min (5 mg s.c twice daily) •Creatinine clearance < 31 ml/min (1.7 mg s.c twice daily)

Sample size	100 patients

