4. INTRODUCTION

4.1. Background

Hirudin is the most potent naturally-occurring direct thrombin inhibitor (DTI), and the first parenteral anticoagulant used on humans.¹

Originally derived from the medicinal leech (*Hirudo medicinalis*), it consists of a 65 amino acids polypeptide chain, forming non-covalent, equimolar, non-reversible 1:1 complexes with α thrombin.¹ When hirudin-bound, thrombin-catalyzed reactions and fibrinogen clotting are blocked, and coagulation is subsequently inhibited.² Hirudin was previously produced in limited amounts, however, recombinant DNA technology allowed its mass production.³ These recombinant forms bind bivalent to thrombin with pharmacokinetic and anticoagulant profile similar to that of the native form.⁴

Recombinant Hirudin is a direct inhibitor of thrombin. It binds in 1:1 ratio with thrombin thus blocking the coagulation cascade and the formation of thrombi.⁵

Unlike heparins, the action of Hirudin is totally independent from any coagulation cofactor that may interfere or alter its action.⁵

Thrombexx is useful in the prevention of thromboembolic complications in at risk patients thrombexx (15 mg) is administered by subcutaneous injection 5-15 minutes before orthopedic or general surgery (after induction of regional block anesthesia) then 15 mg twice daily for 9-12 days and in bedridden patients until patient is fully ambulant (maximum 12 days)⁵

According to the FDA Therapeutic Equivalence Evaluation, 30th Edition, the biosimilar of recombinant hirudin, Desirudin is FDA approved, therefore, the same applies to recombinant hirudin in Egypt.

4.2. Correlative studies:

- 1- Study of Prevention of Thromboembolic with Use of Recombinant Hirudin, Results of a Double-Blind, Multicenter Trial Comparing the Efficacy of Desirudin (Revasc) with That of Unfractionated Heparin in Patients Having a Total Hip Replacement⁶ which showed that desirudin to be more effective than heparin in the prevention of deep vein thrombosis, without any increase in the requirements for transfusion or the risk of hemorrhage. The prevalences of over-all and proximal deep-vein thrombosis in the 174 patients who had been managed with desirudin and were included in the per-protocol analysis were 7 and 3 per cent (thirteen and six patients), respectively.⁶

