6.2. The operative Phase

During this phase, patient's registries for the type of surgery done, Type of anesthesia, patient position and type of prosthesis, & blood transfusion during surgery should be recorded. And IMP dispensing 6 hours after surgery or upon adequate hemostasis will be done. APTT will be done 4 & 8 hours after the first dose

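### Protocol 12.1 as worded orders a dose 8-10 h before spinal puncture, against the trial's own post-operative first dose

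*Protocol*

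**What the plan says.** **Start of treatment.** The synopsis (Study procedures) gives "15 mg BID s.c starting 6 hours after surgery or upon adequate hemostasis and continued until end of study". Protocol 6.2 agrees: "IMP dispensing 6 hours after surgery or upon adequate hemostasis will be done". SAP 2.2 repeats that sentence. Protocol 7.2 lists "Start of IMP administration" under the operative phase (Day 0), after the surgical data. In the flow chart in 7.1, the row "IMP Administration" is marked from Day 0 onward and is blank under the pre-operative phase.

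**Spinal anesthesia.** Protocol 12.1, under the dose heading, adds one sentence for these patients: "Thrombexx will be given 8-10 hours before puncture/catheter and 2-4 hours after puncture/catheter manipulation or removal, as per European Guidelines". The SAP has no corresponding text.

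**Label.** Protocol 4.1, citing the package insert, describes the label regimen as a dose "5-15 minutes before orthopedic or general surgery (after induction of regional block anesthesia) then 15 mg twice daily for 9-12 days". For patients confined to bed, it continues treatment until they can walk freely, with a ceiling of 12 days. SAP 1.1 says the same. The trial dose in the synopsis and in 12.1 is "15 mg twice daily, subcutaneous for 15 days". Protocol 6.1 and SAP 2.1 say that the regimen is decided by standard clinical practice or follows the local marketing authorization for dose, population and indication. They close with a parenthesis placing it within the approved label.

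**The concern.** The first dose is the anchor of this protocol's dosing schedule, and the documents give two incompatible instructions for it in patients having spinal anesthesia. Site staff who follow 12.1 as worded give an anticoagulant before a neuraxial puncture; staff who follow 6.2 give nothing until after surgery. Protocol 15.2.1 bars deviations without prior written sponsor approval, except in medical emergencies, and requires all deviations to be reported to the ethics committee. On the literal wording, either course therefore departs from one of the two sections. Spinal cases are foreseeable, since 12.1 provides for them and type of anesthesia is a recorded item. The documents do not give their share.

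The label reference raises a different and smaller question. A reader of 6.1 or SAP 2.1 could take the whole regimen to be on-label, when its start and its length both differ from the label regimen printed in 4.1.

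**Working it through.** There is no stated figure to reproduce. The check sets the texts side by side and adds some short arithmetic.

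**1. The dose before puncture.**

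| Source | When the first dose falls | Spinal exception? |
|---|---|---|
| Synopsis, 6.2, SAP 2.2 | 6 h after surgery or on adequate hemostasis | None |
| 7.2 | Operative phase, Day 0 | None |
| 7.1 | No mark before Day 0 | None |
| 12.1 (spinal) | 8-10 h before puncture, if read literally | It is the spinal rule |

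Puncture for spinal anesthesia comes before surgery. A dose 8-10 h before it is therefore pre-operative, and no assumption about operating time is needed. Neither part of the start rule can accommodate it, because both are post-operative. The Day 0 entries are supporting evidence only, since with a late puncture such a dose could still fall on the day of surgery. The start rule in the synopsis, 6.2 and SAP 2.2 decides the matter. The label as cited in 4.1 does not support the literal reading either: its pre-operative dose comes after the regional block has been induced.

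**2. The dose 2-4 h after.** Let D be the hours from puncture to end of surgery (not given in the documents).

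- The 6 h point lies D + 6 h after puncture.
- A dose 2-4 h after a single puncture precedes that point by (D + 6) - 4 = D + 2 h to (D + 6) - 2 = D + 4 h.
- The start rule also allows dosing on adequate hemostasis. If D is assumed to be 1 h, a dose 2-4 h after puncture is 1-3 h after surgery, which is permitted once hemostasis is adequate.
- If the interval runs from a later catheter removal, there need be no conflict at all.

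This half conflicts only when hemostasis is not yet adequate and the interval is not counted from a later catheter removal.

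**3. The sentence read as a spacing rule.** Twice-daily dosing leaves 24 / 2 = 12 h between doses. A catheter removal between two doses needs the wait before it plus the wait after it:

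| Before (h) | After (h) | Total (h) | Against 12 h |
|---|---|---|---|
| 8 | 2 | 10 | fits |
| 8 | 4 | 12 | fits |
| 10 | 2 | 12 | fits |
| 10 | 4 | 14 | 14 - 12 = 2 h delay |

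The choice within each range therefore matters, and 12.1 does not make it. The guideline that could settle it cannot be identified: Section 19 has seven references, and the only guideline among them is American.

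**4. Label.** Length: 15 - 12 = 3 days beyond the upper limit in 4.1. That maximum is attached to bedridden patients, but the general range also ends at 12 days. Start: after surgery in the trial, 5-15 minutes before it in the label as cited.

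**The case against.** The strongest reply is that nobody would read 12.1 as an order to dose. Catheter manipulation and removal are events during ongoing treatment, the appeal to European guidelines suggests an interval rule, and the rest of the plan points to a post-operative start. On that reading no patient is dosed before surgery. This stands as an account of intent. It does not repair the sentence, which says that the drug will be given at those times. With a post-operative start, the part about waiting before puncture can apply only to a later procedure, and the sentence does not say that either.

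Three stronger inferences are tempting, and the documents do not support them:

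- **That 12.1 exposes patients to a demonstrated hazard.** Whether a dose 8-10 h before puncture is unsafe depends on a guideline that is not available here. The documents show a contradiction on a safety-relevant point, not a harm.
- **That the early APTT results in SAP Table 10 will mix pre-operative and post-operative samples.** This would follow only if some patients were actually dosed before surgery, which the likely intent excludes. There is no case for splitting the table.
- **That the plan breaks a promise of label compliance.** Protocol 6.1 and SAP 2.1 offer standard practice as an alternative and name dose, population and indication, but neither start nor duration. Both regimens are printed openly. The label is visible only through the 2004 insert, and a later one could differ.

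**Conclusion.** The concern holds for the wording of 12.1. Its instruction to dose 8-10 h before spinal puncture contradicts the post-operative first dose in the synopsis, 6.2 and SAP 2.2, together with the Day 0 start in 7.2 and the empty pre-operative cell in 7.1. This conclusion rests on the text alone. The second half of the sentence is only a conditional conflict.

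No sample size, endpoint or analysis is affected. The defect is a contradictory dosing instruction about an anticoagulant near a neuraxial procedure, and it should be corrected because it is cheap to remove and should not depend on staff guessing the intent.

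The label wording is a separate, minor correction that changes nothing the trial does. The difference is a post-operative start and 3 days beyond the 12-day limit, assuming that the label is as cited in 4.1.

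**What to change.** **Protocol 12.1.** Replace the spinal sentence with a spacing rule, for example: *No dose is given before surgery. In all patients the first dose is given 6 h after surgery or once hemostasis is adequate, and no sooner than X h after the most recent puncture or catheter removal. Any later puncture, or manipulation or removal of a catheter, takes place no sooner than Y h after the last dose; the next dose follows no sooner than X h after it.* The sponsor should take a single value for Y (from 8-10 h) and for X (from 2-4 h) from the guideline it relies on, and add that guideline to Section 19. A range cannot serve as a minimum.

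**Protocol 6.1 and SAP 2.1 (minor).** Delete the closing reference to the approved label, or state that the post-operative start and the 15-day course differ from the 9-12 day regimen cited in 4.1. If a later label supports the trial regimen, cite it.

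**Cost.** One wording amendment, approved by the ethics committee as Protocol 15.2 requires, a matching edit to SAP 2.1, and one added reference. With 10 h and 4 h, one dose is delayed by about 2 h around each catheter removal; the other three combinations cost no delay. If the sponsor does intend a pre-operative dose in spinal patients, the change is larger: the exception must be written into the synopsis, 6.2, 7.1, 7.2 and SAP 2.2.
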